#### b. Secondary Objectives

- To assess the viral load in the nasopharynx and oropharynx before and after application of 0.6% PVP-I of participants of this study.
- To assess the duration of effectivity of 0.6% PVP-I on mucosal surface of participating COVID-19 patients by testing consecutive sample hourly upto 4hr.
- To estimate the shelf-life and stability of 0.6 % PONS.
- To characterize raw materials and impurities for product development and quality control/ assurance
- To measure the safety level of  $0.6\% \underline{PONS}$  by biochemical analysis of participants blood & urine

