## Methodology

#### Study design

It will be a Multicentre, Single blind, Randomized Controlled Trial.

The participant will be divided into three groups namely Group A (384 intervention group and 384 control group), Group B (20 patient) and Group C (10 healthy person).

**Group A** Number of participants 768 COVID-19 positive, moderately ill admitted patient who will receive intervention once (2 puff 0.6% PVP-I in each nostril and 2 puff inside mouth).

Step 1: Enrollment of the study populations by applying inclusion and exclusion criteria

Step 2: Randomization to allocate experimental and controlled group by using table of random number

Step 3: Application of 0.6% PVP-I spray to experimental group and distilled water to control group

Step 4: Follow up (waiting for 2-5 minutes)

Step 5: Collection of nasopharyngeal and oropharyngeal sawab for RT-PCR test for both group

Step 6: Observation of the patients for 30 minutes for possible early adverse effects (if any) and subsequent management (if needed).

Step 7: Analysis data collection, data processing and analysis by using SPSS software.

**Group B** Number of participants 20 asymptomatic to mild COVID -19 patients to whom after single time application of PVP-I oro-nasal spray, RT-PCR test will be done hourly for 4 hours in a single day (to assess the duration of effectiveness of PVP-I oronasal spray).

Step 1: Selection of 20 patients randomly with no or mild symptoms and obtain their consent for the further tests.

Step 2: Collection of 2nd, 3rd and 4th sample from nasopharynx and oropharynx hourly

Step 3: Data collection, data processing and analysis by using SPSS software

**Group C** Number of participants 10 healthy individual who accept intervention 0.6% PVP-I oronasal spray 3-4 hours interval but not more than 4 times a day for 30 days.

Step 1: Selection of 10 healthy volunteers randomly who will be selected for using 0.6% PVP-I Oro-Nasal spray 2 puff inside both nostrils and mouth 3 to 4 times a day for one month.

Step 2: Collection of blood & urine of participants on day 0, 10, 20, 30 for determination of any change in biochemical marker (thyroid, kidney and liver functions will be done)

Step 3: Data collection, data processing and analysis by using SPSS software

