#### N.B.

• Patient with moderate symptoms are normally get admitted in Hospital, who will be included in Group-A.

The intervention Group-A will receive Oronasal spray containing PVP-I and control group will receive distilled water containing oronasal spray.

As all participants of Group-A (asymptomatic, mild, moderate) are included in the study, so they will receive the same treatment (PONS)

- Asymptomatic and mild patients having co-morbid conditions are also admitted in Hospital who will be included in Group-B.
- For Group-C Participants, pre-intervention investigation will be done (FT3, FT4 TSH etc).

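### Group B has no water-spray comparator at hours 1 to 4, so a Ct that stays raised cannot be reported as duration of PVP-I effect

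*Protocol*

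**What the plan says.** The Protocol's Secondary Objectives include this one: "To assess the duration of effectivity of 0.6% PVP-I on mucosal surface of participating COVID-19 patients by testing consecutive sample hourly upto 4hr". Study design assigns the task to Group B, described as "Number of participants 20 asymptomatic to mild COVID -19 patients to whom after single time application of PVP-I oro-nasal spray", and for whom "RT-PCR test will be done hourly for 4 hours in a single day (to assess the duration of effectiveness of PVP-I oronasal spray"). The Group B steps then list the 2nd, 3rd and 4th "sample from nasopharynx and oropharynx hourly".

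Study design sets the allocation as "Group A (384 intervention group and 384 control group), Group B (20 patient) and Group C (10 healthy person"), so only Group A is given a control arm. The N.B. under the selection criteria agrees: "The intervention Group-A will receive Oronasal spray containing PVP-I and control group will receive distilled water containing oronasal spray". In Group A both arms are swabbed once, after "Follow up (waiting for 2-5 minutes"). Group B is characterised in the same N.B.: "Asymptomatic and mild patients having co-morbid conditions are also admitted in Hospital who will be included in Group-B".

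The readout is the Ct value, which the N.B. after Study design calls semiquantitative and inversely related to the amount of viral genetic material in the sample. Neither Data Analysis in the Protocol nor section 2 of the SAP assigns a test, an adjustment or a repeated-measures model to Group B.

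**The concern.** The objective asks for how long PVP-I acts, which is an effect of the product. Group B records what Ct does after the product in people who are also swabbed repeatedly at the same sites. Three things besides PVP-I could raise Ct systematically over those hours: removal of virus-bearing material by earlier swabs, rinsing by the spray liquid, and a trend over time. The sponsor uses a water spray in Group A, and that deals with the liquid and the elapsed time at 2 to 5 minutes. Group B covers a longer period and adds repeated swabbing, but has no such comparator.

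Followed as written, a Ct that remains high at hours 1 to 4 would be reported as hours of effectiveness, and Group B is the trial's only evidence on that question. A good pre-spray value would not cure this, because change from baseline would still combine product, swabbing and time.

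**Working it through.** **1. Is there a controlled swab at hours 1 to 4?**

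| | Group A, PVP-I | Group A, water | Group B |
|---|---|---|---|
| Spray | PVP-I | distilled water | PVP-I |
| Patients | 384 | 384 | 20 |
| Post-spray swabs | one, after 2-5 min | one, after 2-5 min | hourly, up to 4 h |

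The relation between the groups is not fully clear. Group B's steps refer to further tests and number the samples from the second, so Group B may continue from Group A, with its first sample being the 2-5 minute swab. On that reading the first sample has a concurrent water control. On either reading, the hourly samples do not.

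**2. The plan's own sample-size figure.** n = 1.96² × 0.5 × 0.5 / 0.05² = 384.16, which reproduces the stated 384. It is a precision formula for one proportion, applied to each Group A arm. No calculation is given for Group B's 20.

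**3. How often would an inert spray look effective?** The documents give no Ct SD, no non-drug shift and no test for Group B, so this is an illustration.
- Assumed: a one-sample t test of change, n = 20, two-sided 0.05, critical value 2.093 on 19 df; SD of within-person change 2, 3 or 4 cycles; true drug effect zero.
- Formula: non-centrality = shift × √20 / SD; rejection probability = P(|T₁₉| > 2.093) under the non-central t.
- Example: shift 1, SD 2 gives 1 × 4.472 / 2 = 2.236 and a rejection probability of 56%.

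| Non-drug shift (cycles) | SD 2 | SD 3 | SD 4 |
|---|---|---|---|
| 0 | 5% | 5% | 5% |
| 0.25 | 8% | 6% | 6% |
| 0.5 | 19% | 11% | 8% |
| 1 | 56% | 29% | 19% |
| 2 | 99% | 81% | 56% |

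At about two-fold per cycle, a 1-cycle shift means half the recoverable material has gone, and a 2-cycle shift three-quarters. If a concurrent water arm has the same shift, the between-arm test stays at about 5%.

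**4. What would a 10:10 split of the same 20 patients give?** Half-width of the 95% interval = 2.101 × SD × √(2/10), on 18 df.
- Change from a pre-spray swab, SD of change 3 (assumed): 2.101 × 3 × 0.447 = 2.8 cycles. For comparison, the single arm of 20 gives 2.093 × 3 / √20 = 1.4.
- Raw Ct, between-patient SD 5 or 6 (assumed): 4.7 or 5.6 cycles.
- Difference detectable with 80% power: (1.960 + 0.842) × √(2/10) = 1.25 SD by the normal approximation, or 1.32 SD by the t distribution. At SD 3 the latter is about 4.0 cycles.
- Power for a true 2-cycle difference at SD 3: 29%.

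**The case against.** A 20-patient descriptive series is a recognisable exploratory choice. Duration is one of five secondary objectives, it does not appear among the endpoints, and Utilization of Results makes no claim about it. No passage says that Group B sets the application interval. All of this stands and limits the weight of the point. It does not remove it, because both the objective and the stated purpose of Group B claim duration of effect, not description.

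The size is also assumption throughout. Small shifts give rejection rates barely above 5%, and nothing in the documents says how large depletion or rinsing would be. That is correct. The table shows sensitivity and does not estimate an error rate for this trial.

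Four stronger readings are tempting, and the documents or the arithmetic do not support them:

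- *Nothing at all is controlled after 5 minutes.* Group A Step 6 observes patients for 30 minutes for adverse effects and does not restrict this to one arm. The gap concerns swabs.
- *Group A's water arm is unusable because its patients are sicker.* Study design does call Group A moderately ill, but the N.B. under the selection criteria also counts asymptomatic and mild patients in it. The mismatch is unsettled. The reason that holds is timing: water patients are not swabbed hourly.
- *Natural fluctuation produces false effects.* Fluctuation without a trend only widens the interval and leaves the error rate at 5%. Only a systematic shift biases the result.
- *The hourly series carries no information.* Depletion pushes Ct upward, so a Ct that falls again despite repeated swabbing would point to waning that depletion does not mimic. The ambiguity lies mainly in a Ct that stays high.

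**Conclusion.** The point holds in limited form. Group B is a single PVP-I arm, and no water-sprayed patient is swabbed after the 2-5 minute Group A sample, so a persistently raised Ct at hours 1 to 4 cannot be attributed to PVP-I. This follows from the design and needs no assumed number.

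How misleading the result could be depends on a non-drug shift that the documents do not give. Over assumed shifts of 0.25 to 2 cycles and SDs of 2 to 4 cycles, the chance that an inert spray looks significant runs from 6% to 99%; with no shift it is 5%. The objective is secondary, but Group B is its only source of data. The wording should therefore be changed, because that costs almost nothing and alters what the trial may conclude. Adding a comparator is a matter of judgement.

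**What to change.** **If Group B stays single-arm:** reword the duration item in Secondary Objectives and the Group B purpose in Study design as a description of Ct over 4 hours after one spray. State that no duration of effectiveness will be concluded from it. The cost is protocol wording only.

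**If a duration claim is to be kept:** randomise the same 20 patients 10:10 to PONS or the existing distilled-water spray, with identical hourly swabs in both arms. Compare the arms over all hours in one repeated-measures model, so that separate hourly tests do not accumulate. Use change from a same-day pre-spray swab if one is taken; Group B's steps list none, so it would be an added sample. Otherwise this needs an allocation list and a model specification, with no more patients or hourly tests.

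The price is precision, and the Protocol should say so: about 80% power only for a difference of about 1.3 SD, and a half-width of about 2.8 cycles at an assumed SD of change of 3, or about 4.7 to 5.6 if raw Ct is compared at an assumed between-patient SD of 5 to 6. It should also state that a non-significant hour must not be read as the end of the effect. Recruiting 20 per arm would bring the detectable difference down to about 0.89 SD (2.802 × √(2/20), normal approximation), at the cost of 20 more patients and their swabs.

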#### **10. Undesirable effects**

No significant side effect is reported when recommended dose is administered at defined frequency. Mild irritation and burning sensation for few seconds to minutes may be observed. Anaphylactic reactions, anaphylactoid reactions and anaphylactic shock have been reported uncommonly with products containing Povidone-Iodine or Povidone. Excess Iodine can produce goitre and hypothyroidism or hyperthyroidism. Such effects have occasionally been seen with extensive or prolonged use of Povidone Iodine.

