#### • Clinical Laboratory Measurements

#### Blood Chemistry Profile

Blood sample for Group - C participants will be collected and sent to the respective hospitals/BRICM clinical chemistry lab for determining of TSH, FT3, FT4, Serum creatinine, alanine aminotransferase (ALT/SGPT) level including urine test.

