#### Secondary Endpoints:

- Patient is to be safe with no significant side effect after using this oronasal spray.
- Safe if participants of the study who will use 0.6% PONS with minimum side effect (if any)

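### The secondary endpoints are side effects, but the only scheduled adverse-effect observation follows the swab in single-spray Group A; Group C, the only repeated-use group, schedules blood and urine alone

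*Protocol*

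**What the plan says.** **Endpoint.** Both items under Secondary Endpoints in the protocol are about side effects. The second reads "Safe if participants of the study who will use 0.6% PONS with minimum side effect (if any").

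**Safety objective.** The Secondary Objectives section measures safety through blood and urine biochemistry and names nothing else.

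**Expected effects.** Section 10, Undesirable effects, names mild irritation and burning lasting seconds to minutes, uncommon anaphylactic reactions, and goitre, hypothyroidism or hyperthyroidism from excess iodine. Of the thyroid effects it says "Such effects have occasionally been seen with extensive or prolonged use of Povidone Iodine".

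**Collection steps (Study design).**
- Group A (384 active, 384 control): one application, a 2-5 minute wait (Step 4), the swabs (Step 5), then Step 6: "Observation of the patients for 30 minutes for possible early adverse effects (if any").
- Group B (20 patients): one application followed by hourly swabs. No adverse-effect step is listed.
- Group C: "Selection of 10 healthy volunteers randomly", who use the spray "2 puff inside both nostrils and mouth 3 to 4 times a day for one month". Step 2 is "Collection of blood & urine of participants on day 0, 10, 20, 30 for determination of any change in biochemical marker". Step 3 is a general data collection and analysis step.

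The Blood Chemistry Profile gives the Group C panel: "determining of TSH, FT3, FT4, Serum creatinine, alanine aminotransferase (ALT/SGPT) level including urine test".

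**Analysis.** The protocol's Data Analysis section and SAP section 2 list general tests. Neither specifies a side-effect summary or comparison.

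**The concern.** The endpoint asks about side effects, while the objective and the Group C schedule supply laboratory values. No test on the panel detects nasal or oral irritation, or an enlarged thyroid as a physical sign. A volunteer with persistent local irritation but normal TSH, creatinine and ALT would have nothing in the scheduled data to show it. The Utilization of Results section intends to encourage public use on the strength of the safety finding, and Group C is the only group that resembles such use.

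Group A is the only randomised comparison, and so the best source of tolerability evidence. Its observation is placed where an effect lasting seconds to minutes may already be over, and where irritation from the spray cannot be told apart from irritation from the swab.

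**Working it through.** **1. The plan's own figure.** The Sample Size section gives n = Z²pq/d² = 1.96² × 0.5 × 0.5 / 0.05² = 384.16, stated as 384 per Group A arm. It reproduces. It is used below only to count exposure.

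**2. Exposure per Group C volunteer.** The maximum is "3-4 hours interval but not more than 4 times a day for 30 days": 4 × 30 = 120 applications. At 3 times a day, the lower end in Step 1, it is 3 × 30 = 90, taking one month as 30 days.

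**3. Share of active exposure.**
- Group C: 10 × 90 = 900 to 10 × 120 = 1,200 applications.
- Groups A and B: 384 + 20 = 404 active applications.
- Share in Group C: 900/1,304 = 69.0% to 1,200/1,604 = 74.8%.

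This counts applications, not independent observations: all of the Group C exposure sits in ten people.

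**4. Named effects against scheduled collection.**

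| Effect named in section 10 | Group A | Group B | Group C |
|---|---|---|---|
| Local burning or irritation | Step 6, after wait and swab | none scheduled | none scheduled |
| Anaphylactic reaction | Step 6, after wait and swab | none scheduled | none scheduled |
| Hypo- or hyperthyroidism | single spray | single spray | TSH, FT3, FT4 on days 0, 10, 20, 30 |
| Goitre as a physical sign | single spray | single spray | none scheduled |

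**5. Dilution in Group A.** Let s₁ and s₀ be the probabilities of spray-related irritation in the active and control arms, and w the probability of swab irritation, equal in both arms and independent of the spray. The probability of any irritation in an arm is 1 − (1 − s)(1 − w) = w + s(1 − w). The arm difference is then (1 − w)(s₁ − s₀), so the true difference shrinks by the factor (1 − w). The documents give no w. Purely as an assumption, w from 0.2 to 0.6 would leave 80% to 40% of the difference. The direction follows from the model; the size is unknown.

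**6. What ten volunteers can show with full collection.**
- With 0 of 10 affected, solving (1 − p)¹⁰ = 0.05 gives p = 1 − 0.05^(1/10) = 25.9% as the one-sided 95% upper bound.
- The chance of seeing at least one case is 1 − 0.95¹⁰ = 40% at a true rate of 5%, and 1 − 0.90¹⁰ = 65% at 10%.

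**The case against.** **General instruments exist.** Data Collection instrument and Technique provides a questionnaire, a check list, face-to-face interview and a CRF for the whole study, and Group C Step 3 mentions data collection apart from blood and urine. Annexure 3, the CRF, is not in the text supplied and may hold side-effect items. This stands in part. A reader might infer that local effects and goitre will be missed in Group C, but the documents support only that their collection is not scheduled. The instruments as described name no side-effect item and no time point.

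**Supervision and recognition of reactions.** The Risk Management Plan keeps volunteers under close supervision, and section 7 lists signs of immediate hypersensitivity. Some events would surface this way. These passages describe recognition and care, and set no form, time point or grading for recording.

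**Thyroid risk is monitored.** This stands for hypo- and hyperthyroidism. A reader might infer that thyroid harm in general goes uncollected, but the panel and its four days contradict that. Nor do the documents say that goitre would appear within 30 days; the point is only that no examination for it is named.

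**Group A.** Step 4 is labelled as follow-up, patients are directly supervised, and burning felt then could be reported in Step 6. The brief burning is also called mild, while the first endpoint concerns significant side effects. All of this is fair. It means that short burning may be lost, not that it must be. A reader might also infer that the swab erases any arm difference; the difference shrinks by (1 − w) and vanishes only as w approaches 1.

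**Ten people are too few anyway.** True, as the 25.9% bound shows. That limits any conclusion from Group C, and is a reason to collect symptom data from all ten rather than to do without it.

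**Conclusion.** The point holds in this form: the side-effect endpoint and the collection schedule do not match. The one scheduled adverse-effect observation follows the wait and the swab in a single-spray group. The repeated-use group, with 90-120 applications per person and 69-75% of all active applications, has no scheduled record of local irritation and no check for goitre as a physical finding. As written, the plan cannot support a side-effect conclusion for repeated use.

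It does not follow that such effects would go wholly unnoticed, that thyroid dysfunction is unmonitored, or that the Group A comparison is biased by a known amount. The conclusion rests on the steps as listed and on Annexure 3 being unseen, so confidence is medium. The efficacy result is not affected. The matter should be corrected, because the secondary safety conclusion depends on it.

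**What to change.** Reconcile the Secondary Objectives, the Study design steps and the Secondary Endpoints, so that side effects are collected as well as biochemistry.

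- **Group A:** record adverse effects from the moment of spraying through the existing 30-minute observation. Mark onset as before or after the swab in both arms, and use pre-swab onset for local tolerability.
- **Group B:** record from the spray, before the first post-spray swab, and then at each hourly sample. Checking only at swab times would repeat the delay and the swab confounding.
- **Group C:** complete a fixed checklist of the section 10 effects (burning or irritation, allergic signs, goitre by symptom and neck inspection) at the existing day 0, 10, 20 and 30 visits, with day 0 as baseline. Add a simple daily symptom tick-sheet so that brief burning does not rest on 10-day recall.
- **Reporting:** list Group C results per person, and state that 0 of 10 affected leaves a one-sided 95% upper bound of 25.9%.
- **If Annexure 3 already holds these items:** cite it in the Study design steps with its time points.

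The cost is one CRF page, a few minutes at contacts that already take place, and a daily tick from ten volunteers (10 × 30 = 300 entries). No dose, visit or sample size changes.

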#### Side effect

#### 7. Contraindications

#### Iodine hypersensitivity

Patients with sensitivity to iodine and polyvinylpyrrolidine should not receive treatment with povidone-iodine. (ref)

Before intervention all participants will be asked about any H/O hypersensitivity of any drug or food or Iodine containing food or drug. If any participant had previous H/O hypersensitivity he/ she will be excluded from the study.

For immediate hypersensitivity (like other food and drugs) could be ascertained by manifestation of hypotension, respiratory distress, skin itching, discomfort, mucosal swelling. If any , necessary treatment will be provided to settle the patient. For delayed hypersensitivity different biochemical test , like FT3, FT4, TSH etc. will also be done.

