## **Data Collection instrument and Technique**

A preformed semi structured questionnaire and a check list will be used as data collection instrument. Besides medical history sheet and investigation papers of respective participants will also be used. Face to face interview will also be taken.

After receiving written permission from respective hospital authority and obtaining written informed correct data collection will be started. Study personnel at the site will enter data from source documents corresponding to a subject's visit into the protocol-specific paper CRF(Case report form). Subjects will not be identified by name in the study database or on any study documents to be collected by the principle investigator but will be identified by a site number, subject number and initials.

For paper CRFs: If a correction is made on a CRF, the study staff member will line through the incorrect data, write in the correct data and initial and date the change.

The Investigator is responsible for all information collected on subjects enrolled in this study. All data collected during the course of this study must be reviewed and verified for completeness and accuracy by the Investigator. A copy of the CRF will remain at the Investigator's site at the completion of the study (Annexure 3).

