## **Data Processing**

Everyday in later part of the evening collected data will be scrutinized thoroughly to check its consistency and cohesiveness of nearing quality to entre in draft data which will be saved in computer for future use. At the same time necessary coding, editing and cleaning of data will be done. Collected data will be preserved in master data sheet as per objectives and key variables.

All procedures for the handling and analysis of data will be conducted using good computing practices meeting FDA guidelines for the handling and analysis of data for clinical trials. In this regard latest SPSS software version will be used for statistical analysis.

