## Data Analysis

Data will be analyzed by computer using SPSS software computer program. Descriptive statistical analysis including mean, medium, mode, standard deviation, percentage, frequenc will be analyzed by SPSS. Inferential statistics including chi-square test, t-tes, F-test, Anova, Correlation etc will also be done to find out existence of any significant relationship between variables of this study. An analysis plan will also be prepared considering objectives of the study. Different data will be presented in to the frequency tables, graphs, chart according to the requirements.

Study personnel at the site will enter data from source documents corresponding to a subject's visit into the protocol-specific paper CRF(Case report form). Subjects will not be identified by name in the study database or on any study documents to be collected by the principle investigator but will be identified by a site number, subject number and initials.

For paper CRFs: If a correction is made on a CRF, the study staff member will line through the incorrect data, write in the correct data and initial and date the change.

The Investigator is responsible for all information collected on subjects enrolled in this study. All data collected during the course of this study must be reviewed and verified for completeness and accuracy by the Investigator. A copy of the CRF will remain at the Investigator's site at the completion of the study (Annexure 3).

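### Group C's day 10 and day 20 thyroid results need not be read while dosing continues, no response is tied to a thyroid abnormality, and no sample follows day 30

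*Protocol*

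**What the plan says.** Under Study design in the Protocol, Group C Step 1 has 10 healthy volunteers use "2 puff inside both nostrils and mouth 3 to 4 times a day for one month". The group description gives the period as 30 days and the maximum as four applications a day. Step 2 is "Collection of blood & urine of participants on day 0, 10, 20, 30 for determination of any change in biochemical marker", covering thyroid, kidney and liver function. Step 3 is "data collection, data processing and analysis by using SPSS software". The Clinical Laboratory Measurements section lists the tests: TSH, FT3, FT4, creatinine, ALT and urine.

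Thyroid status is addressed at entry. The N.B. under the selection criteria calls for thyroid tests before the intervention, and the Group C exclusion criteria bar anyone with thyroid dysfunction.

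On risk, section 10 (Undesirable effects) says "No significant side effect is reported when recommended dose is administered at defined frequency". It also says that excess iodine can cause goitre and an under- or over-active thyroid, occasionally seen when use is extensive or prolonged. The Risk Management Plan says physicians will supervise the healthy volunteers closely and that any adverse reaction will be managed free of charge. Ethical Issues and Implication repeats the promise of free treatment and gives participants the right to withdraw.

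**The concern.** Group C is the only group dosed repeatedly: 30 × 3 = 90 to 30 × 4 = 120 applications, against a single use in Groups A and B. Its members are healthy and have no treatment benefit to set against a thyroid disturbance. Such a disturbance can be symptomless and show only in the blood result, so supervision that waits for a complaint may miss it. The day 10 and day 20 samples could catch it, but the plan uses them only as data. A volunteer could develop the condition that would have barred entry and go on spraying.

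The day 30 sample has a related limit. If it is abnormal, nothing planned shows whether the value recovers once the spray stops. That matters for the volunteer, and also for the secondary objective of measuring safety by blood and urine analysis.

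**Working it through.** The documents give no figure for this point. Group C's size of 10 is not derived. The one computed figure, 384 per arm, belongs to Group A (1.96² × 0.5 × 0.5 / 0.05² = 384.16, which agrees) and plays no part here. The check is therefore mainly of the text, with arithmetic on the dosing calendar and on chance findings.

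**Places that could hold the missing rule**

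- Clinical Laboratory Measurements: names the tests, with no limit, reader or action.
- Section 7, Iodine hypersensitivity: for delayed reactions, tests "like FT3, FT4, TSH etc. will also be done". It does not say what follows from a result.
- Data Processing: "Everyday in later part of the evening collected data will be scrutinized thoroughly to check its consistency and cohesiveness". The stated aim is data quality.
- Data Collection instrument and Technique: "All data collected during the course of this study must be reviewed and verified for completeness and accuracy by the Investigator", repeated under Data Analysis. Again the aim is data quality, with no timing relative to the next dose.
- Availability and Retention of Investigational Records: interim reports every three months, longer than the 30-day dosing period.
- Data safety & Monitoring: monitoring visits under GCP, with no mention of Group C results.
- Risk Management Plan: specific responses to irritation (irrigation) and hypersensitivity (antihistamine or steroid), otherwise the general pledge.
- Study design, Group A Step 6: 30 minutes of observation, with management if needed. Group C has no matching step.
- SAP sections 1 and 2: a sample size and a list of generic tests, with nothing on Group C.

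None of these requires a clinical reading of the interim results, attaches a response to a thyroid value, or adds a sample after day 30.

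**Dosing left after each sample**

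The protocol does not say whether dosing starts on day 0 or day 1, or whether blood is drawn before or after that day's doses. The two extremes are:

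- Dosing on days 1–30, sample before the day's doses: days 10–30 = 21 days remain after the day 10 sample, and days 20–30 = 11 days after the day 20 sample.
- Dosing on days 0–29, sample after the day's doses: days 11–29 = 19 days and days 21–29 = 9 days remain.

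At 3 to 4 applications a day:

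- After day 10: 19/30 = 63% to 21/30 = 70% of dosing days; 19 × 3 = 57 to 21 × 4 = 84 applications.
- After day 20: 9/30 = 30% to 11/30 = 37% of dosing days; 9 × 3 = 27 to 11 × 4 = 44 applications.

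The day 30 sample falls 30 − 30 = 0 to 30 − 29 = 1 day after the last dosing day.

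**Chance out-of-range values**

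Assume a reference range that covers 95% of healthy people, independent readings, and no effect of the pre-dosing tests.

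- Days 10 and 20, TSH only: 10 × 2 × 0.05 = 1 of 20 readings.
- Days 10 and 20, TSH, FT3 and FT4: 10 × 2 × 3 × 0.05 = 3 of 60 readings.
- Day 30, all three tests: 10 × 3 × 0.05 = 1.5 of 30 readings.
- Per volunteer over days 10 and 20: 1 − 0.95⁶ = 26% have at least one flag on the three tests, and 1 − 0.95² = about 10% on TSH alone.

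Correlation between readings and the entry tests should lower the per-volunteer figures. Even so, they show that one unconfirmed value is a poor reason to stop.

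**The case against.** The strongest reply is that volunteers are not left without care. Physicians supervise them, adverse reactions are to be managed and treated free, anyone may withdraw, and the trial follows GCP and the Declaration of Helsinki. All of that stands. A reader might infer that the protocol is silent on what happens if thyroid dysfunction appears during dosing. The documents do not support that, because the general pledges are wide enough to cover it. What they lack is a requirement to look at the interim results in time, and a recheck off treatment.

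Second, the risk is not established. The protocol reports no significant side effect at the recommended dose, does not say that 30 days counts as prolonged, and tests the thyroid before dosing. This also stands. A reader might infer that volunteers face a demonstrated thyroid hazard, but the documents give no rate, and it may be low.

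Third, the counts of remaining applications restate the calendar. They do, and they exceed what any rule could prevent, because results take time to return.

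Fourth, the CRF annexure, patient leaflet and consent pages are not in the supplied text and may contain instructions. The point is therefore limited to what is supplied.

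Finally, stopping on a single out-of-range value would lose volunteers by chance from the only 30-day data. That is right, and the fix requires confirmation.

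**Conclusion.** The point holds in a limited form. General supervision and management are promised. But the supplied text does not require the day 10 and day 20 thyroid results to be read while dosing continues, links no response to a thyroid abnormality, and plans no sample after day 30. A symptomless change could pass unnoticed until analysis, and an abnormal final value could go without a check on recovery. This is more than missing detail, because the protocol itself names the effect and already draws the samples that would show it.

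The size can be stated only as a ceiling on avoidable exposure: 57 to 84 applications after day 10 and 27 to 44 after day 20, less whatever is used while results are awaited. This rests on 30 dosing days at 3 to 4 applications a day. It says nothing about how often an abnormality would occur. Planned off-treatment repeats number zero. The change should be made, but the documents do not show that anyone has been or would be harmed.

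**What to change.** Add to Group C Step 2 under Study design:

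- The supervising physician reads the day 10 and day 20 results on receipt and records a continue-or-stop decision on the CRF.
- An out-of-range thyroid value is repeated promptly. The spray is stopped if the repeat confirms thyroid dysfunction, the condition that bars entry to Group C. It is stopped at once, without waiting for the repeat, if the volunteer has symptoms or the physician judges the value clearly abnormal.
- A stopped volunteer still gives the remaining planned samples and is reported among the 10.
- Any thyroid abnormality present at stopping or at day 30 is repeated off treatment until normal or explained, and reported for each volunteer.
- Creatinine and ALT findings are left to clinical judgement.

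The cost is a few sentences, the reading of 10 × 2 = 20 result sets, and a few extra blood tests. Under the 95% range assumption, about 3 + 1.5 = 4.5 of 90 thyroid readings on days 10, 20 and 30 would be flagged by chance. Follow-up of a persistent abnormality has no fixed end. Any volunteer who stops contributes a shorter exposure, but remains in the safety report.
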